10.1 Correlative Studies and Hypotheses

1. Pharmacokinetics: Clearance, half-life, and volume of distribution of the both the hCG and EGF components of urinary hCG when administered to patients with GVHD. This objective tests the hypothesis that as enteropathy improves, the PK profile of both hCG and EGF will change.
2. Hormonal effects: concentrations of hCG, estradiol and progesterone, and testosterone at baseline, and on days 7, 14, 28, and 56 of protocol treatment. This objective tests the hypothesis that any increase in sex hormones induced by the hCG will be reversible and associated with no adverse events.
3. Biomarkers of response in routine clinical laboratory parameters: This objective tests the hypothesis that those receiving HCG will have (a) higher circulating numbers of total lymphocytes, monocyte, platelets, and albumin levels as measured by routine clinical laboratory testing and that all will correlate positively, with HCG treatment and plasma levels of both EGF and hCG.

The following studies detailed below in number 4-7 will be exploratory laboratory studies performed on blood samples collected for the study protocol. At each time point, the following samples will be collected:

For patients ≥ 40 kg

- 60 ml of heparinized blood (green top tubes) for PBMCs, and plasma stored in 15 x 1 ml aliquots.

For patients < 40 kg

- *Collect up to 2 cc/kg to a maximum of 65 ml total blood volume for placed in green top tubes. Plasma will be stored in 1 ml aliquots.*

4. Angiogenic biomarkers of response: This objective tests the hypothesis that higher plasma levels of EGF and VEGF-A and lower levels of follistatin will be observed in those receiving HCG treatment and will correlate with response to treatment.
5. Suppressive/regulatory markers of response: This objective tests the hypothesis that higher blood levels of suppressive/regulatory cytokines cells (IL-10, IL-22 – measured by multiplex array, and regulatory T cells – measured by flow cytometry) will be observed in those receiving HCG treatment and correlate with response to therapy.

6. Inflammatory markers of response: This objective tests the hypothesis that lower blood levels of inflammatory markers (TNF α , IL-6, IL-17, IL-33, – measured by multiplex array) will be observed in those receiving HCG treatment and correlate with response to therapy.
7. Accepted biomarkers of GVHD response: This objective tests the hypothesis that reduced levels of validated biomarkers of GVHD (e.g., TNFR1, REG3 α , ST2, where elevated levels are indicative of poor response – measured by ELISA) will be observed in those receiving HCG treatment and will correlate with response to therapy.
8. Tissue expression of markers of regenerative capacity: This objective tests the hypothesis that tissue expression of EGF, IL-22, IDO, Ki-67 will be higher in patients with complete response to therapy. Analytes will be measured by immunohistochemistry (IHC) performed on slides prepared from gastrointestinal specimens previously collected for clinical purposes. No additional biopsies are required for protocol participation.

Separation of PBMCs and plasma, and enumeration of regulatory T cells by flow cytometry, will be performed by the Translational Therapy Laboratory. ELISAS and multiplex arrays will be performed by the Cytokine Reference Laboratory. IHC will be performed by the Histology core/AHC Bionet.

11 Adverse Event Reporting

Toxicity and adverse events will be classified according to NCI's Common Terminology Criteria for Adverse Events V 4.0 (CTCAE). A copy of the CTCAE can be downloaded from the CTEP home page <http://evs.nci.nih.gov/ftp1/CTCAE/About.html>

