7.1 Arm 1 – High-Risk aGVHD

Standard of care immunosuppression, plus Pregnyl® (hCG supplementation) at assigned dose subcutaneously every other day for 4 doses

If a patient has a toxicity that fits the definition of dose limiting as defined in the phase I section below, the patient will discontinue study treatment.

Continue protocol treatment through day 7. Assess response at day 7:

- **If a complete or partial response**, the patient is eligible to receive Pregnyl maintenance at the same dose twice weekly for 10 doses beginning day 9 to 12. Refer to [section 9](#) for response definitions.
- **If no response**, the patient will be taken off study treatment

Pregnyl® dose level assignment will be done by treatment arm, with Arm 1 independent of Arms 2A and 2B.

For phase I, up to 5 dose levels of Pregnyl® will be tested; however dose levels -1 and -2 will be used only if dose level 1 proves too toxic.

Dose Level	Dose
-2	125 USP hCG/875 pg EGF/m ²
-1	250 USP hCG/1,750 pg EGF/m ²
1 (start)	500 USP hCG/3,500 pg EGF/m ²
2	1,000 USP hCG/7,000 pg EGF/m ²
3	2,000 USP hCG/14,000 pg EGF/m ²

The 1st 2 patients will be enrolled in dose level 1. The next cohort of 2 patients will not begin treatment until all patients in the current cohort have reached day 21 in order to assess for dose limiting toxicity (DLT).

Dose limiting toxicity (DLT) is defined as any of the following occurring by day 21 after the 1st dose of Pregnyl® (phase I component only):

- In males and females: Grade 2-4 thromboembolic event (CTCAE v4) i.e., any thrombosis more severe than a superficial venous thrombosis develops and treatment with anticoagulation is required
- In males and females: Grade 3-4 ascites (CTCAE v4)
- Specific to females: Grade 3-4 ovarian hyperstimulation syndrome, defined as the rapid development of enlarged, cystic, painful ovaries - refer to [section 11.2](#) for CTCAE grading guidance

Each new cohort of 2 patients will be assigned by the study statistician to the most appropriate dose level based on toxicity probabilities set for this study. The MTD will be identified when the total sample size of 20 patients is reached.

For the phase II the dose of Pregnyl will be that identified as the MTD during phase I.

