7.2 Arm 2A – Steroid-Dependent aGVHD

Standard of care immunosuppression, plus Pregnyl® (hCG supplementation) at assigned dose subcutaneously every other day for 7 doses.

If a patient has a toxicity that fits the definition of dose limiting as defined in the phase I section below, the patient will discontinue study treatment.

Continue protocol treatment through day 14. Assess response at day 14:

- **If a complete or partial response**, the patient is eligible to receive Pregnyl maintenance at the same dose twice weekly for 10 doses beginning day 15 to 17. Refer to [section 9](#) for response definitions.
- **If no response**, the patient will be taken off study treatment

Pregnyl® dose level assignment will be done by treatment arm, with Arm 2 independent of Arm 1.

For phase I, up to 5 dose levels of Pregnyl® will be tested; however dose levels -1 and -2 will be used only if dose level 1 proves too toxic.

Dose Level	Dose
-2	125 USP hCG/875 pg EGF/m ²
-1	250 USP hCG/1,750 pg EGF/m ²
1 (start)	500 USP hCG/3,500 pg EGF/m ²
2	1,000 USP hCG/7,000 pg EGF/m ²
3	2,000 USP hCG/14,000 pg EGF/m ²

The 1st 2 patients will be enrolled in dose level 1. The next cohort of 2 patients will not begin treatment until all patients in the current cohort has reached day 21 to assess for dose limiting toxicity (DLT).

DLT is defined as any of the following occurring by day 21 after the 1st dose of Pregnyl® (phase I component only):

- In males and females: Grade 2-4 thromboembolic event (CTCAE v4) i.e., any thrombosis more severe than a superficial venous thrombosis develops and treatment with anticoagulation is required
- In males and females: Grade 3-4 ascites (CTCAE v4)
- Specific to females: Grade 3-4 ovarian hyperstimulation syndrome, defined as the rapid development of enlarged, cystic, painful ovaries—refer to [section 11.2](#) for CTCAE grading guidance

Each new cohort of 2 patients will be assigned by the study statistician to the most appropriate dose level based on toxicity probabilities set for this study. The MTD will be identified when the total sample size of 20 patients is reached.

For the phase II the dose of Pregnyl will be that identified as the MTD during phase I.

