- **Progression:** deterioration of any organ involved.

- **No Response (NR):** absence of any improvement or progression as defined above.

10 Schedule of Patient Activities

Scheduled evaluations after screening and through day 19 of the last treatment cycle may be performed +/-2 days from the targeted date; assessments performed after day 28 and through day 56 may be done +/-5 days of the targeted date. After day 56, assessments will coincide with the post-transplant follow-up schedule (i.e., additional clinic visits specifically for this study will not be required). In addition, targeted days may be altered as clinically appropriate, and will not constitute a protocol deviation.

Schedule of Treatment, Tests and Procedures – Arm 1

	Baseline	Treatment Days +/- 2 days												Phase I only	Follow Up +/- 5 days***	
Procedures, evaluations, and treatment		1	3	5	7	9	11	13	14	15	17	19		21	28	56
Standard of Care																
Vital signs and weight	X	X	X	X	X	X	X	X	X	X	X	X			X	X
Performance status (Karnofsky or Lansky)	X				X				X			X			X	X
Acute GVHD staging	X				X				X						X	X
Complete blood count	X				X				X			X			X	X
Complete metabolic panel	X				X				X			X			X	X
Serum creatinine	X															
Ejection Fraction by echocardiogram or MUGA	X															
Research																
Pregnyl® dosing*		X	X	X	X	*										
Assess for toxicity		beginning with the 1st dose of Pregnyl® and continuing for 4 weeks after the last dose per section 11.2 (if phase I assess for DLT at day 21)														
Pharmacokinetics**		X			X											
Serum hCG	X^				X				X						X	X
Estradiol, progesterone, and testosterone	X				X				X						X	X
Collection of blood samples for immune and tissue damage/repair biomarkers (refer to section 10.3 for blood volume and tube type)s	X				X				X						X	X

MT2014-12: hCG supplementation in high-risk or refractory aGVHD

Research related blood samples will go to Translational Therapy Lab (TTL) for processing and storage until study related testing.

*If a patient achieves a complete or partial response, he/she may continue to receive maintenance Pregnyl® doses twice per week, in the dose level he or she was already assigned, for another 10 doses, beginning during protocol day 9-12.

**Blood samples (2 ml plasma) collected 30 (\pm 10) minutes pre-dose, and at post-dose 1 hour (\pm 5 min), 3 hours (\pm 5 min), 6 hours (\pm 10 min), and 24 hours (\pm 30 min).

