13.3 Statistical Analysis

SAS 9.3 (Cary, NC, USA) will be used for the statistical analyses. For binary endpoints such as toxicity, summary statistics including proportions and their 95% confidence intervals will be calculated for each arm. All toxicity and safety assessments will be presented in the data listings and summarized with descriptive statistics. Response at day 28 will be estimate with simple proportions and descriptive plots.

The secondary endpoint, proportions of response among the surviving patients at day 7, 14, 56 and 180, treatment failure proportion for acute GVHD at day 28, 56 and 180 after initiation of protocol therapy, the incidence of acute GVHD flare after CR/PR requiring increase of steroids or other systemic treatment at days 28, 56, and 180 will be estimated. Overall survival and disease free survival probabilities after the initial treatment will be estimated using Kaplan-Meier's method. Treatment-related mortality and the incidence of chronic GVHD after the initial treatment will be estimated by competing risk analysis. For other correlative endpoints, continuous measures will be summarized with mean and SD for each arm and time point (if skewed, we will report median and interquatile range) and categorical measures will be summarized with frequency and percentage.

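### The day-56 hormone summary mixes patients days off drug with patients weeks off drug, so the reversibility hypothesis cannot be read reliably from it

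*Combined protocol and SAP*

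**What the plan says.** Section 10.1, item 2, sets the hypothesis: "This objective tests the hypothesis that any increase in sex hormones induced by the hCG will be reversible and associated with no adverse events". The measurements are "concentrations of hCG, estradiol and progesterone, and testosterone at baseline, and on days 7, 14, 28, and 56 of protocol treatment". Section 1.3 lists the same days and adds a comparison with baseline. The schedules in section 10 show no hormone draw after day 56.

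Dosing is in section 7. Arms 2A and 2B receive the drug "at assigned dose subcutaneously every other day for 7 doses". In case of a complete or partial response at day 14, "the patient is eligible to receive Pregnyl maintenance at the same dose twice weekly for 10 doses beginning day 15 to 17" (sections 7.2 and 7.3). Arm 1 receives 4 doses, and its day-7 responders may continue "twice weekly for 10 doses beginning day 9 to 12" (section 7.1). Non-responders stop study treatment.

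On timing, section 10 says that "assessments performed after day 28 and through day 56 may be done +/-5 days of the targeted date". It adds that "targeted days may be altered as clinically appropriate, and will not constitute a protocol deviation".

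For correlative endpoints, section 13.3 says that "continuous measures will be summarized with mean and SD for each arm and time point", with median and interquartile range if the data are skewed. It has no split by maintenance status and no term for time since the last dose. The documents define neither reversibility nor a minimum washout.

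**The concern.** A claim that a drug effect reverses needs observations after the drug is stopped, at a known interval. For a patient on maintenance, the draws at days 7, 14 and 28 all fall within the treatment course, so only the day-56 draw can show reversal. That draw is tied to the study calendar, not to the last dose, so the off-drug interval varies between patients.

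The planned summary adds a second problem. Within an arm, patients at day 56 differ together in response status, number of doses and time off drug. The pooled value can look reversed because early-stop patients have been off drug for weeks, or not reversed because maintenance patients were dosed recently. Neither reading would answer the hypothesis for the patients with the most doses at their dose level.

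**Working it through.** **Inputs.** Maintenance start days: 15 to 17 (Arms 2A and 2B) and 9 to 12 (Arm 1), from section 7. Ten doses, twice weekly. Draw window: day 56 ± 5, so days 51 to 61. Last dose if treatment stops at the initial assessment: day 7 (Arm 1) and day 13 (Arms 2A and 2B), from the schedules in section 10.

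**The plan's own figure.** 10 doses ÷ 2 per week = 5 weeks, which matches the additional 5 weeks of therapy in section 7.5.

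**Last dose day.** Twice weekly is taken as alternating 3- and 4-day gaps (an assumption). Ten doses have nine gaps:
- starting with a 3-day gap: 5×3 + 4×4 = 31 days;
- starting with a 4-day gap: 5×4 + 4×3 = 32 days.

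Arms 2A and 2B: 15 + 31 = day 46 to 17 + 32 = day 49. Arm 1: 9 + 31 = day 40 to 12 + 32 = day 44.

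**Days from last dose to last hormone draw** (draw day minus last dose day):

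| Group | Doses | On target (day 56) | Across days 51-61 |
|---|---|---|---|
| Arms 2A/2B, full maintenance | 7 + 10 = 17 | 56−49 = 7 to 56−46 = 10 | 51−49 = 2 to 61−46 = 15 |
| Arm 1, full maintenance | 4 + 10 = 14 | 56−44 = 12 to 56−40 = 16 | 51−44 = 7 to 61−40 = 21 |
| Arms 2A/2B, non-responders | 7 | 56−13 = 43 | 38 to 48 |
| Arm 1, non-responders | 4 | 56−7 = 49 | 44 to 54 |

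**Effect of pooling.** If a share p of the patients sampled at day 56 had maintenance, the arm mean is p × (maintenance mean) + (1 − p) × (early-stop mean). Suppose, for illustration, that early-stop patients are back at baseline and maintenance patients are still raised by x. The pooled rise is then p·x. Borrowing 40% and 65% from section 13.2 only as example values of p, the same residual rise appears as 0.40x or 0.65x. The summary moves with the responder share although nothing about reversal has changed.

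**Is 7-10 days enough?** The documents give no half-life. With assumed half-lives of 1 to 3 days, the share remaining, 0.5^(days ÷ half-life), is 25% to 63% at 2 days, about 1% to 20% at 7 days and 0.1% to 10% at 10 days. The answer turns on a figure that the plan does not supply.

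**One-sided draw, days 56 to 61.** Arms 2A/2B: 56−49 = 7 to 61−46 = 15 days off drug. Arm 1: 56−44 = 12 to 61−40 = 21 days.

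**The case against.** A reader might infer that reversibility is not observed at all in Arm 2 responders, because the last draw can come 2 days after a dose. The documents do not support that. Two days needs the latest start, the longer spacing and the earliest draw together. Of 3 start days × 2 spacings × 11 draw days = 66 combinations, 1 gives 2 days and 4 give 3 days or fewer (a count, not a probability). On target, every patient who completes maintenance has an off-drug sample at 7-10 days in Arms 2A/2B or 12-16 days in Arm 1, and nothing in the documents shows that this is too short.

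Nor are responders the most exposed patients overall. In Arm 2B, a level-5 non-responder nominally receives 7 × 5,000 = 35,000 USP/m², against 17 × 2,000 = 34,000 for a full-course level-3 responder. The statement about exposure holds only within a dose level.

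The plan also has safeguards. Serum hCG is drawn at the same visits as the sex hormones, so residual drug can be seen patient by patient. Section 1.3 already compares with baseline. Section 11.2 monitors gynecomastia and ovarian hyperstimulation separately, so safety monitoring does not rest on this draw. Section 13.3 does not forbid further analyses, and the objective is correlative and descriptive.

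These points stand and limit the claim. They do not repair the summary: the only analysis that section 13.3 specifies still combines patients with very different times off drug, and it does not link the hormone values to hCG or to the date of the last dose.

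**Conclusion.** The concern holds as a problem of interpretation. In patients who complete maintenance, reversal rests on one sample, 7-10 days (Arms 2A/2B) or 12-16 days (Arm 1) after the last dose on target, and 2-15 or 7-21 days across the window. The planned summary pools it with samples taken 43 or 49 days after the last dose, from patients who had 7 or 4 doses instead of 17 or 14. A pooled day-56 value is therefore not a reliable test of the hypothesis in section 10.1.

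This rests on alternating 3- and 4-day gaps, doses given on schedule and all ten maintenance doses received. If the last dose slipped by 2 days, the shortest Arm 2 gap would be 0. It also takes the day-56 draw to apply to non-responders, for whom the schedules make no exception. If they are not sampled, the pooling disappears, but day 56 then describes a different group from the earlier draws.

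The DLT assessment, MTD, response endpoint, stopping rules and sample size are not affected. The change is worth making because it is cheap.

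**What to change.** 1. In section 13.3, report change from each patient's own baseline in hCG, estradiol, progesterone and testosterone, separately for maintenance and early-stop patients and by days since the last dose. State what will count as reversed. This needs only the dates of the last dose and of the draw.
2. In the section 10 schedules, make the day-56 hormone draw one-sided for maintenance patients (days 56 to 61). With doses on schedule this gives at least 7 days off drug in every arm. If the last dose slips by 2 days, the minimum is 56 − 51 = 5. Because target days may be altered without a deviation, the analysis should use actual dates.

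The cost is slightly less scheduling freedom and smaller subgroups in a descriptive summary.

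A further draw 4 weeks after the last dose would be informative but should stay optional, for cases where it coincides with a routine visit. Sections 10 and 11.2 describe a toxicity monitoring period of that length, not a visit with blood sampling, and section 10 says that no study-specific visits are required after day 56.

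Separately, the adverse-event follow-up should be reconciled. Section 7.6 follows patients other than initial non-responders through day 56. Sections 10 and 11.2 run to 4 weeks after the last dose, which for full-course patients is day 46 + 28 = 74 to 49 + 28 = 77 in Arms 2A/2B and day 40 + 28 = 68 to 44 + 28 = 72 in Arm 1.

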11.1 Definitions

Note: throughout this section the generic term “drug” refers to the Pregnyl®, or its generic equivalent, injection.

The following definitions are based on the Code of Federal Regulations Title 21 Part 312.32 (21CFR312.32(a)).

Adverse Event: Any untoward medical occurrence associated with the use of a drug in humans, whether or not considered drug related.

Suspected Adverse Reaction: Any adverse event for which there is a reasonable possibility that the drug caused the adverse event.

Life-Threatening Adverse Event Or Life-Threatening Suspected Adverse Reaction: An adverse event or suspected adverse reaction is considered “life-threatening” if, in the view of either the investigator or sponsor, its occurrence places the patient or subject at immediate risk of death.

Serious Adverse Event Or Serious Suspected Adverse Reaction: An adverse event or suspected adverse reaction is considered “serious” if, in the view of either the investigator or sponsor, it results in any of the following outcomes:

- Death
- A life-threatening adverse event
- Inpatient hospitalization or prolongation of existing hospitalization
- A persistent or significant incapacity or substantial disruption of the ability to conduct normal life functions
- A congenital anomaly/birth defect.

Important medical events that may not result in death, be life-threatening, or require hospitalization may be considered serious when, based upon appropriate medical judgment, they may jeopardize the patient or subject and may require medical or surgical intervention to prevent one of the outcomes listed in this definition.

If either the IND sponsor or the investigator believes the event is life-threatening or serious, the event must be evaluated by the sponsor for expedited reporting (21CRF 312.32(a)).

Unexpected adverse event or unexpected suspected adverse reaction: An adverse event or suspected adverse reaction is considered “unexpected” if it is not listed in the investigator brochure or is not listed at the specificity or severity that has been observed; or, if an investigator brochure is not required or available, is not consistent with the risk information described in the general investigational plan or elsewhere in the current application, as amended. Thus, adverse events that occur as part of the disease process or underlying medical conditions are considered unexpected; however, they will not be reportable per [section 11.4](#).

Major Deviation: A deviation or violation that impacts the risks and benefits of the research; may impact subject safety, affect the integrity of research data and/or affect a subject’s willingness to participate in the research.

Deviations that place a subject at risk, but do not result in harm are considered to be major deviations.

Minor Deviation: A deviation or violation that does not impact subject safety, compromise the integrity of research data and/or affect a subject's willingness to participate in the research.

Expedited (Rapid) Reporting: Certain events may require rapid notification to entities providing patient safety oversight (e.g. IRB, FDA) as detailed in [section 11.4](#). For the IRB this is 5 business days from discovery. For studies under an IND, it is 7 or 15 calendar days.

